13. CLINICAL MONITORING

Pre study visit

- Assess the site's infrastructure (staff and facility) for the capability to conduct the study.
- Evaluate Investigator and staff's Experience, Qualifications and Capabilities-signed and dated CV.

Study Initiation visit

Orients the investigator's staff involved in the study on:

- The study protocol;
- Case report form (CRF);
- HIPAA, GCP and other regulatory requirements;
- Informed Consent Form and process;
- AE, SAE, Safety reporting;
- Subject information - subject's identification log, subject screening log, subject enrollment log, subject study visit log;

Study monitoring;

- Investigator's study files;
- Report of AE back from the Sponsor to the site;
- Expectations from the site regarding data collection and timelines.

Regular Monitoring visits

- Check on the progress of the study;
- Protocol and GCP compliance;
- Informed Consent Form and process;
- CRF completion, correction, source data verification
- AE, SAE, Safety reporting;
- Investigational product;
- Investigator's study files. Detailed monitoring schedule to be provided at study initiation

Final Study visit Close out monitoring visit

- Ensure Investigator understands the on-going responsibilities
- Record archival practices for source documents & CRF's after completion of the study -up to 15 years;
- Follow-up of on-going adverse events - up to 30 days after completion of the study;
- Notify the sponsor in the event of Health Authority inspection.

14. STATISTICAL CONSIDERATIONS

Statistical Design

This study is a randomized, open-label, multi-centre study.

Sample Size

Enrollment will continue until up to 100 evaluable subjects have been recruited to the study. Any subject removed from the study in accordance with the provisions of this protocol will be replaced by other subject.

Statistical Methods

All subjects who received any amount of treatment will be included in the report. The primary outcome measure is the subject's overall tolerability of the adjuvant combination treatment as compared to the standard of care post fractional RF treatment. The self-assessment will be based on a 5-point Likert scale - Subject Tolerability Scale (Appendix A). Summary statistics will be generated for subject tolerability immediately after treatment, 24 hours and 72 hours following

treatment as per the terms: Very tolerable, tolerable, having no opinion, intolerable and very intolerable.

The secondary outcomes measures are the subject's degree of discomfort and/or pain as measured by the visual analogue scale (VAS), the incidence of spontaneous adverse events (AEs) and the investigator's assessment of improvement using the Fitzpatrick Wrinkle and Elastosis Scale scores before and after treatment as well as Global Aesthetic Improvement Scale (GAIS) for each subject. VAS scores from the treated group will be compared with the VAS scores of the standard of care group. The investigator's assessment of improvement using the Fitzpatrick Wrinkle and Elastosis Scale from the treatment group will be compared with that of the standard of care group. The GAIS scores for both groups will also be compared.

Summary statistics will also be generated for all treatment emergent adverse events (TEAs). The following types will be reported:

- Overall TEAEs
- Severe TEAEs
- TEAEs related to treatment
- Serious Adverse Events (SAEs)
- SAEs related to treatment
- TEAEs leading to treatment discontinuation

15. DATA HANDLING and RECORD KEEPING

Confidentiality

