Key Inclusion Criteria	
 • Male or non-pregnant, non-nursing female at least 21 years of age and less than 75 years of age. • Undergoing a dermatological procedure requiring ablation and resurfacing of the facial skin utilizing the Venus Viva™ SR system.
Key Exclusion Criteria	
 • Superficial metal or other implants in the treatment area. • Tattoos, permanent makeup, scars or piercings in the treatment area. • Any active condition in the treatment area, such as sores, psoriasis, eczema and rash.

	
 Any surgical procedure in the treatment area within the last three months or before complete healing.
Primary endpoint	The primary end point will be the tolerability of the application of the stem cell recovery complex (SCR Complex™) and a botanical lipid based occlusive (Bio Cel™) as compared with standard of care immediately following fractional RF treatments.
Secondary endpoints	The secondary outcomes will be the subject's degree of discomfort and/or pain as measured by the visual analogue scale (VAS), the incidence of spontaneous adverse events (AEs) and the investigator's assessment of improvement using the Fitzpatrick Wrinkle and Elastosis Scale scores before and after treatment as well as the Global Aesthetic Improvement Scale (GAIS) for each subject.
Statistical Methodology	
All subjects who received any amount of treatment will be included in the report. The primary outcome measure is the subject's overall tolerability of the adjuvant combination treatment as compared to the standard of care post fractional RF treatment. The self-assessment will be based on a 5-point Likert scale - Subject Tolerability Scale (Appendix A). Summary statistics will be generated for subject tolerability immediately after treatment, 24 hours and 72 hours following treatment as per the terms: Very tolerable, tolerable, having no opinion, intolerable and very intolerable.
 
Summary statistics will also be generated to present the degree of discomfort and/or pain following the procedure, all treatment emergent adverse events (TEAs) and the GAIS scores for the treatment group and standard of care group.

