4. PURPOSE

The purpose of the study is to compare the tolerability of the application of a combination of a serum containing human bone marrow stem cell derived growth factor and cytokines (SCR COMPLEX™) and a botanical lipid-based occlusive (Bio Cel™) immediately following fractional RF treatment using the Venus Viva™ versus standard of care.

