6. PRIMARY ENDPOINT

The primary outcome measure will be the tolerability of the application of the stem cell recovery complex (SCR Complex™) and a botanical lipid based occlusive (Bio Cel™) as compared with standard of care following fractional RF treatments.

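### The trial is randomized to compare tolerability between arms, but no between-arm estimate, confidence interval, primary time or two-session rule is pre-specified for the primary score

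*Combined protocol and SAP*

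**What the plan says.** **The question is comparative.** Section 4 (Purpose) opens: "The purpose of the study is to compare the tolerability of the application of a combination of a serum" and sets the combination against standard of care. Section 14 (Statistical Methods) describes the primary outcome as the subject's "overall tolerability of the adjuvant combination treatment as compared to the standard of care post fractional RF treatment".

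**The analysis is descriptive.** Section 14 then says: "Summary statistics will be generated for subject tolerability immediately after treatment, 24 hours and 72 hours following" treatment, using the five Likert terms. The Synopsis (Statistical Methodology) says the same: "Summary statistics will be generated for subject tolerability immediately after treatment, 24 hours and 72 hours following treatment as per the terms". Nothing further is given for this score.

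**By-arm presentation is implied.** The Synopsis continues: "Summary statistics will also be generated to present the degree of discomfort and/or pain following the procedure", together with adverse events and "the GAIS scores for the treatment group and standard of care group". The word 'also', with the comparative definition of the outcome, makes it reasonable to expect tolerability tables by arm.

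**The endpoint wording does not fix a time.** The Synopsis has "as compared with standard of care immediately following fractional RF treatments", while Section 6 has "as compared with standard of care following fractional RF treatments", without the word 'immediately'. In Section 4 that word describes when the product is applied, not when tolerability is scored.

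**Six scores per subject.** The Schedule of Events, the Synopsis (Study design) and Sections 11.2 and 11.3 together place the scale immediately, at 24 hours and at 72 hours after each of two treatments. The last score is taken at the follow-up visit.

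**The concern.** A randomized control arm is there to provide a contrast. If the plan is followed exactly, it describes each arm but does not say which difference answers the question, on what scale, or with what uncertainty. The secondary outcomes fare slightly better: Section 14 says that the VAS, Fitzpatrick and GAIS results of the two groups will be compared, though it gives no method. It has no matching sentence for the tolerability scores.

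The plan does require all three times and all five terms to be reported, so a time or term cannot simply be left out. What stays open is emphasis: which time, which session, and whether the sessions are combined. Subjects know their allocation and rate themselves, so a contrast chosen after the results are seen would be hard to defend as the trial's answer.

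The choice also has substance, because the times do not measure the same thing:

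- **Immediate score.** Section 11.2 lists it before the step at which the topical combination or standard of care is given. If the list is in sequence, the first-session immediate score precedes the randomized intervention and cannot show its effect.
- **72-hour score.** Section 8 has all subjects resume the same skin care at 24 hours, so a 72-hour contrast reflects an initial difference followed by two days of common care.

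**Working it through.** **1. What the plan can be checked for.** No figure in the plan can be reproduced here. Section 14 gives a ceiling of 100 evaluable subjects, with no alpha, power, effect size, variability or allocation ratio.

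**2. Size of the unspecified choice (from the documents).**
- Scores per subject, and so candidate contrasts: 2 sessions x 3 times = 6.
- Percentages in by-arm tables: 3 times x 5 terms x 2 arms = 30. With the sessions shown separately, 30 x 2 = 60.
- Contrasts named as primary: none. Intervals named: none.

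**3. Which elements are specified for the primary score.**

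| Element | Stated? |
|---|---|
| Comparison intended | Yes (Synopsis; Sections 4, 6 and 14) |
| Times and terms to report | Yes, three and five |
| Tables by arm | Inferred, not explicit |
| Effect measure between arms | No |
| Confidence interval | No |
| Primary time | No |
| Combine, select or split sessions | No |
| Meaning of 'overall' tolerability | No |

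**4. Precision that one named contrast would have (illustration).** The contrast is a common odds ratio across the five ordered levels, from one session. For the log odds ratio, Whitehead's approximation is

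V = n1 x n2 x N / (3(N+1)^2) x (1 - sum of p^3), SE = 1/sqrt(V), factor = exp(1.96 x SE).

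Here n1 and n2 are the arm sizes, N is their sum, and p is the assumed proportion in each category. The 95% CI runs from the odds ratio divided by the factor to the odds ratio multiplied by it.

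Assumptions, none of them in the documents: equal arms of 50 (all 100 subjects, 1:1) or 25, and four score distributions, listed from very intolerable to very tolerable.

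| Assumed distribution | Sum of p^3 | SE, 50 per arm | Factor | SE, 25 per arm | Factor |
|---|---|---|---|---|---|
| .10 .20 .20 .35 .15 | 0.063 | 0.361 | 2.03 | 0.516 | 2.75 |
| .03 .07 .10 .45 .35 | 0.135 | 0.376 | 2.09 | 0.537 | 2.87 |
| .02 .05 .08 .40 .45 | 0.156 | 0.381 | 2.11 | 0.544 | 2.90 |
| .01 .03 .06 .30 .60 | 0.243 | 0.402 | 2.20 | 0.574 | 3.08 |

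Worked example, first row at 50 per arm: V = 50 x 50 x 100 / (3 x 101^2) x (1 - 0.063) = 7.65; SE = 1/sqrt(7.65) = 0.361; factor = exp(1.96 x 0.361) = 2.03.

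**5. Sparse categories.** Under the fourth distribution at 50 per arm, the two lowest categories expect 50 x 0.01 = 0.5 and 50 x 0.03 = 1.5 subjects per arm. An ordinal model therefore needs a merging rule set in advance.

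**The case against.** The strongest reply is that descriptive reporting can be legitimate. This is an open-label tolerability study of at most 100 subjects, and it promises no hypothesis test. With by-arm tables of all five terms at all three times, a reader can compute a risk difference or odds ratio, with an interval, for any single time and session. Much of this stands. No test is required, and it would be too strong to say that the plan yields no estimate. What remains is that no contrast is pre-specified, so the reader can compute several and the report can lead with any of them. If the tables pool the sessions, a valid interval cannot be recovered, because the pairing within subjects is lost.

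A reader might also infer an inflated false-positive rate from picking among six contrasts, or from pooling two sessions as if they were independent. The documents do not support either inference. No test, significance level or success criterion is stated for tolerability, and unadjusted pooling is nowhere proposed. Multiplicity would become an issue only if p-values were produced.

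Finally, a proportional-odds model is one choice among several. The point is that one estimate should be named, not that it must be this one.

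**Conclusion.** The concern holds as an omission in the analysis plan, and it should be fixed. The study's own comparative question has no pre-specified between-arm estimate or interval, no primary time and no session rule, and overall tolerability is undefined. Up to six contrasts are therefore available for the headline.

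This conclusion rests on the text and on no calculated figure. The precision range (a factor of about 2.0 to 2.2 at 50 per arm, 2.8 to 3.1 at 25) shows only the scale of uncertainty that the tables would leave unstated. It depends on assumed arm sizes and score distributions, and on proportional odds.

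Two stronger readings are not supported: that the plan allows times or terms to go unreported, and that it gives no means at all of deriving a difference.

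**What to change.** Before any data are seen, add to Section 14:

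- **Definition.** Define overall tolerability by one primary time and one session rule, for example the score 24 hours after the first treatment. The sponsor chooses, bearing in mind that all subjects return to the same skin care at 24 hours. The immediate score should not be used as evidence of the topical's effect unless the protocol confirms that it is recorded after application.
- **Contrast.** Compare the arms on the five ordered levels, for example by a proportional-odds model with terms for arm and site, and report the common odds ratio with its 95% CI. If categories are sparse, merge the adjacent lowest ones by a rule set in advance.
- **If both sessions are used.** Add a session term, account for within-subject correlation (for example GEE or a subject random effect), and state how missing second-session scores are handled.
- **Other results.** Report the remaining times and sessions as supportive, with intervals.

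The single-session version is cheap: a few sentences and a few lines of code, with no new visits, data or subjects. Using both sessions takes somewhat more work, for the correlated-data model and the missing-score rule. The real cost to the sponsor is giving up the freedom to headline a different time or session.

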5. STUDY DESIGN

This is a randomized, open-label, multi-centre study to evaluate the tolerability of the application of a combination of a serum containing human bone marrow stem cell derived growth factor and cytokines (SCR Complex™) and a botanical lipid based occlusive (Bio Cel™) following facial fractional RF

treatments using the Venus Viva™ SR system.

Subjects will be asked to attend up to four visits to the clinic: Screening/consultation, 2 treatment visits - 3 weeks apart and 1 follow-up (FU) visit 3 days after the last treatment. Subjects will also receive a telephone call to evaluate response at 24 hours after each treatment as well as 72 hours after the first treatment. The first treatment visit may occur on the same day as the screening visit. RF treatments will be conducted as detailed in the Venus Viva™ User Manual. For each subject, study duration will be approximately 30 days, including study follow-up. It is anticipated that the study will start July 2016 with an anticipated stop date of September 2016. Changing of these dates will not require a protocol amendment.

Up to 100 healthy subjects from 2 centres who meet the inclusion and exclusion criteria will be enrolled and randomized to the study. The trial will be conducted in compliance with the protocol, GCP and the applicable regulatory requirements. The Sponsor, Venus Concept, will maintain oversight and management of the study.

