- Refusal of the subject to continue treatment and/or observations
- Decision by the Investigator that termination is in the subject's best medical interest
- Device failure
- Subject is lost to follow-up
- Other ethical or clinical considerations

Subjects will be recruited through chart review from the investigator sites, referrals or any type of media advertising. All screened subjects will be recorded on a screening log. Any information given to subjects and any advertisements intended for use for this study must be approved by the site's ethics board prior to use.

10. DEVICE and INVESTIGATIONAL PRODUCTS

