11.3 Follow-up/Termination Visit

Subjects will be scheduled for a follow-up/termination visit 72 hours after the second treatment. The following procedures will be performed:

- The subject will be asked to report on the comfort(s)/discomfort(s) associated with the second treatment as per the Self-Report Adverse Event Questionnaire.
- Wrinkle evaluation (Fitzpatrick Wrinkle and Elastosis Scale)
- Global Aesthetic Improvement (GAI) Scale (Appendix D) as evaluated by the investigator.
- Subject Tolerability Scale 72 hours post second treatment
- Assessment of concomitant medications

The subject's participation in the study is now complete. In case of early termination, the date and reason for early termination will be recorded in the CRF. Subjects will also be asked to return to the clinic to complete follow-up/termination visit procedures.

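### Does the tolerability summary need a rule for treatment-2 scores missing after refusal, a definition of evaluable, and a reconciled limit of 100?

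*Combined protocol and SAP*

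**What the plan says.** The primary outcome is the subject's rating on a five-point tolerability scale, adjuvant combination against standard of care. Each subject is due two treatments three weeks apart (Synopsis; Section 11.2). The analysis is one sentence in Section 14: "Summary statistics will be generated for subject tolerability immediately after treatment, 24 hours and 72 hours following" treatment, by response category. The population is stated just before it: "All subjects who received any amount of treatment will be included in the report".

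On numbers, Section 14 says "Enrollment will continue until up to 100 evaluable subjects have been recruited to the study" and "Any subject removed from the study in accordance with the provisions of this protocol will be replaced by other subject". The Synopsis also applies the 100 to evaluable subjects. Section 5 says "Up to 100 healthy subjects from 2 centres who meet the inclusion and exclusion criteria will be enrolled and randomized to the study".

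On leaving the study, Section 9 lists "Refusal of the subject to continue treatment and/or observations" among the grounds on which a subject may be removed. At the termination visit (Section 11.3) the only tolerability item is "Subject Tolerability Scale 72 hours post second treatment". For early terminations, "the date and reason for early termination will be recorded in the CRF", and the subject is asked back to the clinic.

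**The concern.** A subject who refuses the second session has no treatment-2 score at 0, 24 or 72 hours, and no later visit can supply one. In a tolerability trial, refusal may itself reflect intolerance. If so, and if intolerance at the first session predicts intolerance at the second, a percentage of available treatment-2 scores understates intolerance. The trial is open-label, so refusal could also differ by arm and distort the comparison in either direction. With no stated rule, the denominator could be chosen after the data are seen.

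Two further gaps sit beside this one. Evaluable sets the recruitment target but is never defined. Replacing every removed subject until 100 are evaluable cannot be squared with at most 100 randomised once that number is reached and a removal has to be replaced.

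**Working it through.** **No figure to reproduce.** The ceiling of 100 has no alpha, power, effect size or dropout rate behind it. All rates below, and 50 per arm (1:1), are assumptions.

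**1. What is lost.** Only treatment-2 scores are lost for certain. The immediate treatment-1 score is taken in clinic. Treatment-1 home forms are handed in at the next visit (Appendix A), so they are lost only if the subject never returns.

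**2. Denominator effect.** Suppose 10 of 50 in an arm have no treatment-2 score and 34 of the remaining 40 rate treatment as tolerable:
- observed scores: 34/40 = 85.0%
- missing counted as not tolerable: 34/50 = 68.0%
- missing counted as tolerable: (34 + 10)/50 = 88.0%

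The choice matters at that level of loss, but a table showing 40 scored and 10 missing lets a reader derive all three.

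**3. Bias in available scores, and the composite alternative.** Let p be treatment-1 intolerance; a and b treatment-2 intolerance among treatment-1-intolerant and treatment-1-tolerant subjects; r the share of intolerant subjects who refuse. Tolerant subjects do not refuse. Setting b = (p − pa)/(1 − p) keeps the true treatment-2 rate at p.

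- Available rate = [p(1 − r)a + (1 − p)b] / [p(1 − r) + (1 − p)]
- Composite rate (refusal counted as unfavourable) = pr + p(1 − r)a + (1 − p)b

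With p = 0.20 in both arms, and r = 0.25 in one arm and 0.75 in the other:

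| a / b | Available, r = 0.25 | Available, r = 0.75 | Gap (points) | Composite, r = 0.25 | Composite, r = 0.75 | Gap (points) |
|---|---|---|---|---|---|---|
| 1 / 0 | 15.8% | 5.9% | 9.9 | 20% | 20% | 0 |
| 0.6 / 0.1 | 17.9% | 12.9% | 5.0 | 22% | 26% | 4 |
| 0.2 / 0.2 | 20% | 20% | 0 | 24% | 32% | 8 |

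Middle row at r = 0.75: available = (0.03 + 0.08)/0.85 = 12.9%; composite = 0.15 + 0.03 + 0.08 = 26%. Last row at r = 0.75: composite = 0.15 + 0.01 + 0.16 = 32%.

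The available-score gap falls with the intolerance rate: 5.0, 2.8 or 0 points at p = 0.10, and 2.5, 1.4 or 0 at p = 0.05. Pooling both treatments at p = 0.20 gives 4.4, 2.2 or 0. A true difference can also be masked. True rates of 20% and 10%, with 60% and 10% of intolerant subjects refusing, show a gap of 0 (full persistence) or 5.1 points (a = 0.6) instead of 10.

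**4. Sampling error for scale.** 95% half-width of a difference at 20% with 50 per arm: 1.96 × √(2 × 0.2 × 0.8/50) = 0.157, or 15.7 points.

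**5. The ceiling of 100.** Randomised subjects needed for 100 evaluable are 100/(1 − w), rounded up, where w is the share removed: 106 at 5%, 112 at 10%, 125 at 20%. Stopping at 100 randomised leaves 95, 90 or 80. With 90 evaluable, or 45 per arm, the half-width becomes 1.96 × √(2 × 0.2 × 0.8/45) = 0.165, or 16.5 points instead of 15.7. Because the 100 is a ceiling, the texts do not always clash: 90 randomised, 5 removed and 5 replaced makes 95, within both.

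**The case for a change.** The strongest case for a change is that a primary percentage needs a denominator even in a descriptive analysis. Missing scores here may be informative about the outcome itself, and an open-label trial with no rule leaves room to choose one after seeing the results. The remedy would be cheap: some wording, a disposition table and perhaps one CRF field. The bias is below sampling error, but a confidence interval does not reflect it.

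Much of this stands. No section of the public text gives a missing-score rule, and asking early leavers back is data collection, not an analysis rule. What does not stand is the claim that there is no denominator at all. Section 14 names all treated subjects as those reported; only the detail by treatment and time point is absent. Nor does replacement cause the bias, since removed subjects who were treated stay in the report.

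The information needed to read the result is largely collected. The reason for early termination goes in the CRF, reasons for missed procedures go in source documents (Section 15), and Section 14 reports adverse events leading to treatment discontinuation. The adverse event definition in Section 12 is broad and discomfort is among the anticipated events, so many intolerance refusals should appear there. Refusals not recorded as an event would not.

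**Conclusion.** No change follows. The first gap is missing detail that an analyst fills sensibly: tabulate by arm, treatment and time point among treated subjects, with the number missing and the recorded reason. Treatment-1 summaries are largely unaffected, and no test, power claim or success criterion depends on the treatment-2 denominator.

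The one substantive alternative, scoring refusals as unfavourable, is a trade-off. It removes the bias when intolerance fully persists between sessions. When the two sessions are unrelated, it creates an 8-point gap (32% versus 24%) from equal true rates, where available scores show none. The documents give no basis for choosing between these cases.

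The wording on the ceiling of 100 and the undefined term are drafting slips. They conflict only if 100 are already randomised and a removal must then be replaced, and reconciling them changes no stated figure or result.

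This rests on assumed rates. A false gap of 9.9 points requires 20% intolerance, full persistence and 75% versus 25% refusal; at 5% intolerance it is at most 2.5 points under the same refusal pattern. Requiring subjects to tolerate a test spot (Section 9) and allowing energy settings to be modified between visits (Section 11.2) may keep refusals few. Heavy refusal that differed by arm would make the treatment-2 summaries hard to interpret, but the counts would show it.
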